**Table 3 - Summary of primary estimands for main endpoints**

Endpoint Category (estimand)	Endpoint	Population	Estimands	Population-level summary (Analysis and missing data handling)
Primary safety objective: To assess the tolerability and to confirm the recommended dose of tusamitamab ravtansine in combination with ramucirumab in the NSQ NSCLC population				
Primary endpoint (primary estimand 1)	Study drug-related dose-limiting toxicity at Cycle 1 and Cycle 2, by dose level (if applicable).	DLT-evaluable population	Participants from the DLT-evaluable population will not experience any anticipated intercurrent events before experiencing a DLT at Cycle 1 or at Cycle 2 or before completing the Cycle 2, whichever is earlier.	Incidence of study drug-related DLTs at Cycle 1 and Cycle 2, defined as rate of participants with study-drug related DLTs at Cycle 1 and Cycle 2.
Primary efficacy objective: To assess the antitumor activity of tusamitamab ravtansine in combination with ramucirumab in the NSQ NSCLC population				
Primary endpoint (primary estimand 2)	Confirmed objective response (confirmed CR or PR as BOR), determined according to RECIST 1.1	All-treated population restricted to participants treated at the RP2D.	Regardless of IMP discontinuation (treatment policy strategy).  Based on tumor assessments done before initiation of further anticancer therapy ("while not initiating anticancer therapy" strategy)	Objective response rate, defined as rate of participants with confirmed objective response and two-sided 95% confidence interval (CI) using the Clopper-Pearson method.  In the absence of confirmed objective response, participants will be considered as non-responders, whatever the reason (including participants with non-evaluable BOR).

## 2 SAMPLE SIZE DETERMINATION

The safety run-in part aims to establish the RP2D of tusamitamab ravtansine in combination with ramucirumab according to DLTs observed.

Part 2 of this study is designed to obtain preliminary efficacy, safety, and PK data on tusamitamab ravtansine administered in combination with ramucirumab to participants with NSQ NSCLC. As the second part is not intended to explicitly test a hypothesis, calculations of power and Type I error were not considered in the study design.

Assuming a pre-screening failure rate of 80% and a study screening failure rate of 20%, approximately 225 participants will be pre-screened to achieve a total of up to approximately 36 treated participants, including Part 1 (safety run-in) and Part 2 of the study.

Sample size of the safety run-in part:

The actual sample size is expected to vary depending on DLTs observed. It is anticipated that around 6 to 12 DLT-evaluable participants (as defined in Section 3) will be enrolled in the safety run-in part of the study.

Sample size of Part 2:

The initial plan is to treat a total of 30 participants evaluable for activity (ie, having at least one post-baseline evaluable tumor assessment, early clinical progression, or death due to disease progression). The 6 participants treated at the RP2D in the safety run-in part will also be evaluable for this second part of the study.

Estimated ORR and 95% exact CIs by number of responders from a sample size of 30 participants evaluable for activity are summarized in Table 4.

**Table 4 - Estimated objective response rate depending on number of responders**

Number of Responders (N=30)	Objective Response Rate in % (95% Clopper-Pearson CI)
6	20.00% (7.71% - 38.57%)
8	26.67% (12.28% - 45.89%)
9	30.00% (14.73% - 49.40%)
11	36.67% (19.93% - 56.14%)
12	40.00% (22.66% - 59.40%)

### 3 ANALYSIS POPULATIONS

The following populations for analyses are defined:

**Table 5 - Populations for analyses**

Population	Description
Pre-screened	All participants who signed the pre-screening informed consent for CEACAM5 assessment of their biopsy.
Screened	All participants who signed the screening informed consent for study participation.
Enrolled	Participants from screened population who have been allocated to intervention regardless of whether the intervention was received or not.
All-treated	All enrolled participants exposed to the study treatment, regardless of the amount of treatment administered. All safety analyses will be performed on this population, which is also the primary population for analysis of all efficacy parameters.
DLT-evaluable (Part 1)	All enrolled participants who received 2 cycles with at least 80% of the intended dose for both tusamitamab ravtansine and ramucirumab at each of the two first infusions unless they discontinued the study intervention before the end of Cycle 2 due to a DLT.
Activity	All-treated participants who have measurable disease at study entry and at least 1 post-baseline evaluable tumor assessment. Participants with no post-baseline evaluable tumor assessment but with an early clinical progression or who died due to disease progression will also be included in this set. This population is the secondary population for analysis of efficacy parameters.
PK	All participants from the all-treated population with at least 1 post-baseline PK concentration with adequate documentation of dosing and sampling dates and times.
ATA	All participants from the all-treated population with at least 1 post-baseline ATA result (negative, positive, or inconclusive).
Population without trial impact (disruption) due to COVID-19	All treated participants: 

Without any critical or major deviation related to COVID-19

And who did not permanently discontinue study intervention due to COVID-19

And who did not permanently discontinue study due to COVID-19

ATA = anti-therapeutic antibodies; CEACAM5 = carcinoembryonic antigen-related cell adhesion molecule 5; DLT = dose-limiting toxicity; PK = pharmacokinetic.

In practice, a participant will be included in the enrolled population if the question “Will the subject continue in the treatment phase?” has been answered as “Yes” in the “Completion of screening phase” e-CRF page.

In practice, a participant will be included in the DLT-evaluable population (applicable to Part 1 only) if a “Dose Limiting Toxicities” e-CRF page has been filled in at the end of Cycle 1 and at the end of Cycle 2 (or Cycle 1 only if participant did not receive Cycle 2 because of a DLT). This includes participants followed up to the end of the DLT observation period or participants having experienced a DLT before the end of the DLT observation period and validated by the Study Committee. Participants with an overdose (defined as a dose received at least 30% above the intended dose) of tusamitamab ravtansine or ramucirumab at any of the two first infusions will be excluded from the DLT-evaluable population.

Participants treated with study intervention before or without being enrolled will not be considered enrolled and will not be included in any analysis population. The safety experience of these participants will be reported separately.

Enrolled participants for whom it is unclear whether they took the study intervention will be considered as treated and will be included in the all-treated population.

For any participant enrolled more than once, only the data associated with the first enrollment will be used in any analysis population. The safety experience associated with any later enrollment will be reported separately.

In practice, participants whose BOR is nonevaluable due to minimum criteria for SD duration not met (ie, overall response of SD and the minimum duration, defined as  $0.75 \times$  duration between the first IMP intake and the first planned tumor assessment is not met) and there is no subsequent evaluable tumor assessment, or documented PD after two or more nonevaluable tumor assessments (ie, overall response of PD and the time between the date of first IMP intake and the documentation of PD is greater than the theoretical planned date of the second tumor assessment) will be considered as not evaluable for the activity population.

## 4 STATISTICAL ANALYSES

### 4.1 GENERAL CONSIDERATIONS

This study is not intended to explicitly test a hypothesis. 95% confidence intervals will be provided for primary and secondary efficacy endpoints.

All efficacy endpoints based on radiological assessments of tumor burden (ie, confirmed objective response, PFS and DOR) will be derived using the local radiologist's/Investigator's assessment.

In general, continuous data will be summarized using the number of observations available, mean, standard deviation (SD), median, Q1, Q3, minimum, and maximum. Categorical and ordinal data will be summarized using the count and percentage of participants.

The baseline value is defined as the last available value before the first dose of IMP.

The study cut-off for analysis of the primary efficacy endpoint, ORR, corresponds to the date on which all evaluable treated participants have had at least 2 post-baseline tumor assessments, experienced confirmed objective response, or have discontinued the study for any reason, up to approximately 6 months (4 months for 2 tumor assessments and 2 months for confirmation of response, if needed) from the date of the last participant's first IMP administration.

The analysis cut-off date is defined as the date of the database extraction that will be performed for the analysis.

#### *Observation period*

The observation period will be divided into 4 segments:

- The **pretreatment period** is defined as the period up to the first IMP administration.
  - The **prescreening period** is defined as the period from the pre-screening informed consent or addendum to informed consent (for participants with available CEACAM5 result) to the day before the screening informed consent.
  - The **screening period** is defined as the period from the screening informed consent up to the first IMP administration.
- The **on-treatment period** (ie, **treatment-emergent period**) is defined as the period from the first IMP administration to the last IMP administration + 30 days.
- The **posttreatment period** is defined as the period from the end of the on-treatment period.

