1.3 SCHEDULE OF ACTIVITIES (SOA)

1.3.1 Study flow chart - Doublet cohort

Procedure	Pre-screening ^a	Screening ^b	Treatment cycle 1		Treatment cycle 2 +		End of treatment	90 (± 7) Days (3 month) Follow-up ^d	Notes*
Day		Days to first infusion	D1		14 (± 2) days from previous infusion		30 (± 5) days from last infusion		
			Pre-infusion ^c	EOI	Pre-infusion ^c	Every 8 weeks (± 7 days)			
CEACAM5 expression status ^a (archival or fresh tumor tissue) – central IHC/ prescreening Informed consent	X								
Informed Consent		X							
Inclusion/exclusion criteria		≤ 28	X						Section 5.1, 5.2
Demography, medical/surgical/disease/smoking history ^e		≤ 28							
NSCLC characteristics ^f	X	≤ 28							
Height		≤ 7							
Performance status (ECOG)		≤ 7	X		X		X	X	Section 8.2.1, 8.2.3
Physical examination, including vital signs, body weight ^g		≤ 7	X		X		X	X	Section 8.2.1
Hematology ^h		≤ 7	X		X		X		Section 8.2.5, 10.2 (Appendix 2)
Coagulation ⁱ		≤ 7	X		X		X		Section 10.2, (Appendix 2)
Clinical blood chemistry ^j		≤ 7	X		X		X		Section 8.2.5, 10.2 (Appendix 2)
Urinalysis ^k		≤ 7	X		X				Section 10.2, (Appendix 2)
HBsAg & HCV serology and HIV test (only if required at country level)		X							Section 10.8, (Appendix 8)

Procedure	Pre-screening ^a	Screening ^b	Treatment cycle 1		Treatment cycle 2 +		End of treatment	90 (± 7) Days (3 month) Follow-up ^d	Notes*
Day		Days to first infusion	D1		14 (± 2) days from previous infusion		30 (± 5) days from last infusion		
			Pre-infusion ^c	EOI	Pre-infusion ^c	Every 8 weeks (± 7 days)			
Urine or Serum pregnancy test ^l		≤ 7			X		X	X	Section 10.2 (Appendix 2) Section 10.5 (Appendix 5)
Left ventricular ejection fraction (MUGA/echocardiogram) ^m		≤ 28							Section 8.2.4.2
12-lead ECG ⁿ		≤ 7	X	X	X		X		Section 8.2.4.1
Specific ocular tests ^o		≤ 28					X		Section 8.2.2
Tusamitamab rvtansine/Ramucirumab administration			X		X				Section 6.1
AE assessment ^p	X		Continuously throughout the study period						Section 8.2, 8.3, 10.3 (Appendix 3)
Concomitant medication ^q		X	Continuously throughout the study period						Section 6.5
Tumor assessment – RECIST v1.1 - CT/MRI; relevant surrogate markers ^r		≤ 28				X	X	X	Section 8.1
Circulating CEA ^s	X	≤ 28				X	X	X	
IgG			X						
Record further anticancer therapy								X	
Tusamitamab rvtansine and ramucirumab PK			Refer to PK/ATA flowchart, Section 1.3.3						Section 8.5
Tusamitamab rvtansine Immunogenicity			Refer to PK/ATA flowchart, Section 1.3.3						Section 8.9

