- h Hematology: Hemoglobin, hematocrit, RBC, WBC with differential, platelet counts. These tests will be done before IMP administration at each cycle. If Grade 4 neutropenia, assess absolute neutrophil count (ANC) every 2-3 days until ANC $\geq 0.5 \times 10^9/L$. During first 2 cycles, hematology will be performed weekly.
- i Coagulation: International normalized ratio (INR), aPTT.
- j Clinical blood chemistry: Liver function tests: SGOT (AST), SGPT (ALT), total bilirubin, conjugated bilirubin, AP. Renal function tests: Urea (or BUN) & creatinine. Electrolytes: Sodium, potassium, calcium, glucose. Others: LDH, albumin and total proteins. During first cycle, liver function tests will be performed weekly. The liver function tests and renal function tests will be done before IMP administration at each cycle, unless clinically appropriate. In case of Grade ≥ 3 liver function abnormal tests, additional tests will be repeated every 2-3 days until recovery to baseline value.
- k Urinalysis tests on morning spot will be performed by dipstick at baseline, and at every treatment cycle. In case of proteinuria $\geq ++$ (dipstick), proteinuria quantification by proteinuria/24 h should be performed.
- l Serum pregnancy test: women of childbearing potential must have a negative serum pregnancy test result within 7 days prior to the initial dose of IMP. A pregnancy test (serum/urine) will be repeated every 4 weeks before IMP administration, and a serum test will be repeated at the End of Treatment evaluation (30 \pm 5 days after the last IMP administration), and at the Follow-up visit (90 \pm 7 days after last IMP dose).
- m Echocardiogram or MUGA scan: left ventricular ejection fraction (LVEF) will be evaluated during screening period, and whenever clinically indicated.
- n 12-lead ECG is required at baseline (In case the ECG performed less than 7 days before 1st IMP administration is considered as normal, there is no need to repeat it just before the 1st IMP) before starting the and after completing the first IMP administration (within 30 minutes after the end of tusamitamab ravtansine infusion). The ECG after the infusion at cycle1 should be performed at any case; before IMP administration at each cycle; and at the End of treatment evaluation, 22 to 30 days after last IMP administration.

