The study cut-off for the secondary ORR endpoint analysis of triplet cohort corresponds to the date on which all evaluable treated patients have had at least 2 post baseline tumor assessments, experienced confirmed objective response, or have discontinued the study for any reason. This study cut-off will occur approximately 4.5 months after the date of the first IMP administration of the last participant: 3 months for 2 tumor assessments and 1.5 months if a confirmation of response is needed.

Disclosure Statement:

This is an open-label, single-arm, 2 cohorts study in patients with previously treated metastatic NSQ NSCLC.

Number of participants:

In the doublet cohort, approximately 225 participants will be prescreened (CEACAM5 prescreening failure rate is 80% and study screen failure rate is 20%) to achieve up to approximately 36 treated participants.

In the triplet cohort, approximately 74 participants will be prescreened to achieve up to approximately 12 DLT evaluable participants, based on the doublet cohort CEACAM5 prescreening failure rate of 79% and an estimated study screen-failure rate of 23%.

Intervention groups and duration:

The duration of the study for a participant will include a period for screening of up to 28 days. Once successfully screened, enrolled participants may receive study intervention until disease progression, unacceptable AE, or the participant's or investigator's decision to stop the treatment. Each cycle of treatment will have a duration of 2 weeks in the doublet cohort and 3 weeks in triplet cohort. After discontinuing study intervention, participants will return to the study site approximately 30 (± 5) days after the last IMP administration or before the participant receives another anticancer therapy, whichever is earlier, for end-of-treatment assessments; additionally, a final safety follow-up visit will be scheduled 90 days after the last dose of IMP. The expected duration of study intervention for participants may vary, based on progression date; median expected duration of study per participant is estimated as 11 months (1 month for screening, a median of 6 months for treatment, and a median of 4 months for end-of-treatment follow-up). The total estimated duration of enrollment will be approximately 12 months.

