8.3 ADVERSE EVENTS AND SERIOUS ADVERSE EVENTS

8.3.1 Adverse events, treatment-emergent adverse events, and adverse events of special interest

The safety profile of the IMP will be based on incidence, severity (as graded by the NCI CTCAE V5.0), and cumulative nature of TEAEs. TEAEs are defined as AEs that develop, worsen or become serious during the on-treatment period. For this study, the on-treatment period will be defined as the period from the time of first dose of IMP to at least Day 30 of the last tusamitamab ravtansine administration. Each patient will be assessed preferably by the same physician for AEs and according to the NCI CTCAE V5.0 classification.

An AESI is an AE (serious or nonserious) of scientific and medical concern specific to the Sponsor's product or program, for which ongoing monitoring and immediate notification by the Investigator to the Sponsor is required. Such events may require further investigation in order to characterize and understand them. Adverse events of special interest may be added, modified or removed during a study by protocol amendment.

- Pregnancy of a female subject entered in a study as well as pregnancy occurring in a female partner of a male subject entered in a study with IMP/NIMP;
 - Pregnancy occurring in a female participant entered in the clinical trial or in a female partner of a male participant entered in the clinical trial. It will be qualified as an SAE only if it fulfills one of the seriousness criteria (see Appendix 3 [[Section 10.3](#)]).
 - In the event of pregnancy in a female participant, IMP should be discontinued.

- Follow-up of the pregnancy in a female participant or in a female partner of a male participant is mandatory until the outcome has been determined (See Appendix 5 [Section 10.5]).
- Grade ≥ 3 keratopathy
- Bundle branch blocks or any conduction defects.
- Grade ≥ 3 liver enzyme increased (symptomatic or asymptomatic)
- Symptomatic overdose (serious or nonserious) with IMP/NIMP
 - An overdose (accidental or intentional) with the IMP/NIMP is an event suspected by the Investigator or spontaneously notified by the participant and defined as at least 30% above the intended administered dose at each cycle expressed in unit per body surface or unit per weight.
- All protocol-defined DLT (Section 4.1).

The definitions of an AE or SAE can be found in Appendix 3 (Section 10.3).

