9.4.2 Safety analyses

All safety analyses will be performed on the all-treated population for the Part 1 (safety run-in part) and Part 2 of the doublet cohort, and for the triplet cohort, by dose level and overall. Summary of Safety data will be performed by participant. For each safety parameter, a baseline value will be defined as the last value or measurement taken up to the first administration of the IMP.

A summary of safety analyses is provided in [Table 17](#).

Table 17 - Safety analyses

Endpoint	Statistical Analysis Methods
Primary	
For the doublet cohort: Incidence of study drug-related dose-limiting toxicity (DLTs) at Cycle 1 and Cycle 2	Descriptive statistics
For the triplet cohort: Incidence of study drug-related DLTs at Cycle 1	
Secondary	
Incidence of TEAEs and SAEs and laboratory abnormalities according to NCI CTCAE V5.	Descriptive statistics
Incidence of ATAs against tusamitamab raptansine (SAR408701)	Will be described in the SAP
Exploratory	No exploratory endpoint is defined for safety analyses.

ATA=anti-therapeutic antibodies; TEAE=treatment emergent adverse event; SAE=serious adverse event; SAP=statistical analysis plan.

The observation period will be divided into 4 segments:

- The prescreening period is defined as the time from when the participants give prescreening informed consent or provide an addendum to informed consent (for participants who already have available CEACAM5 expression result) to the day before the screening informed consent.
- The screening period is defined as the time from when the participants give screening informed consent to the first administration of the IMP.

- The treatment period is defined as the time from the first administration of IMP up to 30 days after the last administration of IMP.
- The post-treatment period is defined as the time from the 31st day after the last administration of IMP to study closure or death, whichever occurs first.

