### **Analyses according to potentially clinically significant abnormalities (PCSA) and NCI grading**

For laboratory variables, analyses according to NCI grading will be made based on NCI-CTCAE Version 5.0. In addition, for laboratory variables for which the NCI-CTCAE scale is not applicable, such as vital signs and ECG variables, PCSA analyses will be performed based on the PCSA list currently in effect at Sanofi at the time of the database lock.

Analyses according to PCSA and NCI grading will be performed based on the worst value during the treatment-emergent period, using all measurements (either local or central, either scheduled, nonscheduled or repeated).

QTcF prolongation will be graded according to NCI-CTCAE version 5.0. The frequency of participants each grade of QTcF prolongation during the on-treatment period will be summarized. For participants with multiple occurrences of QTcF prolongation during the treatment, the maximum grade per participant will be used.

For laboratory variables, vital signs and ECG variables above, the incidence of participants with at least one PCSA during the treatment-emergent period will be summarized regardless of the baseline level and according to the following baseline status categories:

- Normal/missing
- Abnormal according to PCSA criterion or criteria

The number (%) of participants with QTcF abnormality worsening during the on-treatment period (worst value per participant) will be displayed.

For laboratory variables graded by NCI-CTCAE,

- The number (%) of participants with abnormal laboratory tests at baseline will be presented by grade.
- The number (%) of participants with an abnormal laboratory test during the treatment-emergent period will be summarized by grade. When appropriate, the number (%) of participants with abnormality of any grade and with Grade 3-4 abnormalities will be provided.
- For liver function test abnormalities, the baseline status will be provided according to multiples of the upper limit of normal (ULN) for each test.

For laboratory variables graded neither by NCI-CTCAE nor by PCSA, the number (%) of participants with laboratory test results outside normal ranges will be provided.

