##### ***Visual acuity test***

Analyses are done on the best corrected visual acuity assessed using Snellen Chart method.

Frequency tables on best corrected visual acuity (BCVA) measured during on-treatment period will be performed separately on all participants and on participants who experienced at least one treatment-emergent corneal event:

- On the worst change from baseline: No worsening versus baseline (no line decrease), Worsening versus baseline 1 to 3 lines decrease versus baseline, or  $> 3$  lines decrease versus baseline).
- On the worst absolute value: No change versus baseline, Worsening versus baseline (BCVA equals to 20/40 or better, BCVA worse than 20/40 up to 20/200, BCVA 20/200 or worse).
- On the CTCAE worst vision decrease: BCVA equals to 20/40 or better or 1 to 3 lines decrease versus baseline, BCVA worse than 20/40 up to 20/200 or  $> 3$  lines decrease versus baseline, BCVA 20/200 or worse.
- For participants who had worsening versus baseline on BCVA (at least one line decrease), the worst outcome on the last BCVA value will be displayed: Recovered to baseline, Not recovered to baseline, Lost to follow-up or dead with ongoing corneal events.

Of note, a participant will be considered as lost to follow-up, if the participant discontinued the study and did not perform any follow-up visit.

A shift table of the category of the last BCVA value (Normal (20/20 or better), worse than 20/20 up to 20/40, worse than 20/40 up to 20/200 or 20/200 or worse) versus the category of the worst BCVA value (20/40 or better, worse than 20/40 up to 20/200, 20/200 or worse) will be performed for participants who experienced at least one treatment-emergent corneal event.

For the summary table on participants who experienced at least one treatment-emergent corneal event, the worst value and the worst change from baseline are measured during any of the treatment-emergent corneal events experienced by the participant (between start date and end date of the corneal events). For the summary table on all participants, all on-treatment BCVA values are considered.

The worst classification between the laterality is considered for the worst value, the worst change from baseline and the last separately even if not measured on the same eye. If the worst absolute value is the same for both eyes, then the eye with the worst change from baseline is considered, and if identical, then the eye with the worst last value is considered.

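### The SAP's day-30 cut-off leaves laboratory values from a compliant End-of-Treatment visit on days 31-35 out of the worst-on-treatment tables; worst vital signs and one set of visual acuity tables are also affected

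*SAP*

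**What the plan says.** SAP 4.1 (Observation period) states that the on-treatment, or treatment-emergent, period "is defined as the period from the first IMP administration to the last IMP administration + 30 days"; whatever follows is post-treatment. Protocol 9.4.2 draws the same line: "The post-treatment period is defined as the time from the 31st day after the last administration of IMP". Protocol 8.3.1 words it differently, running the period "to at least Day 30 of the last tusamitamab ravtansine administration".

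The doublet flow chart (protocol 1.3.1) places the EOT visit at "30 (± 5) days from last infusion". Protocol 4.1 gives "approximately 30 (± 5) days after the last IMP administration or before the participant receives another anticancer therapy, whichever is earlier". Hematology, coagulation, chemistry, vital signs, ECG and ocular tests are all marked in the EOT column. The ECG also has its own timing in footnote n: "and at the End of treatment evaluation, 22 to 30 days after last IMP administration". Protocol 8.2.4.1 repeats those ECG days.

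SAP 4.7.3.1 performs the NCI-grade and PCSA analyses "based on the worst value during the treatment-emergent period, using all measurements". SAP 4.7.3.2 introduces the visual acuity tables with "Frequency tables on best corrected visual acuity (BCVA) measured during on-treatment period will be performed".

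**The concern.** The visit window is symmetric around day 30 and the analysis window stops at day 30. Two participants can both attend on a permitted day, and only one has the EOT values counted. What decides it is the calendar day of the visit.

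This matters most for laboratory values. The incidence of laboratory abnormalities is a secondary endpoint, and EOT is the last scheduled hematology and chemistry draw, because the 90-day follow-up column has neither. SAP 4.7.3.1 plans by-visit descriptive statistics for vital signs and ECG only. An abnormality first seen, or first reaching its worst grade, at a day-33 draw would therefore be missing from the graded tables and would not show in a by-visit table either.

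**Working it through.** **Inputs**
- End of on-treatment period: last IMP + 30 days (SAP 4.1; protocol 9.4.2).
- EOT visit: 30 ± 5 days (protocol 1.3.1 and 4.1).
- EOT ECG: days 22 to 30 (protocol 1.3.1 footnote n; 8.2.4.1).
- Treated participants: 30 to 36 (SAP 1.1). The upper figure reproduces from the screening assumptions in SAP section 2: 225 × 0.20 × 0.80 = 36.

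**Day count**
- EOT window: 30 − 5 = 25 to 30 + 5 = 35, which is 11 days.
- Days after the cut-off: 31, 32, 33, 34, 35, which is 5 of 11.
- ECG window, days 22 to 30: 0 days after the cut-off. It overlaps the visit window only on days 25 to 30.
- If the period for scheduled measurements ran to last IMP + 35 days, 0 of the 11 EOT days would fall outside.

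**Is there a rule that rescues a day 31-35 visit?** None was found. The only visit-handling convention, SAP 5.3, lets unscheduled measurements count toward worst treatment-emergent values. It does not lengthen the period.

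**Which analyses lose the value?**

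| Measurement | Analysis rule in the SAP | Day 31-35 EOT value |
|---|---|---|
| Laboratory grades, PCSA | Worst value in the treatment-emergent period | Lost; no by-visit laboratory table |
| Vital signs, worst value | Same | Lost |
| Vital signs, by visit | Each planned visit | Not stated to be cut |
| BCVA, all participants | On-treatment values | Lost |
| BCVA, participants with a treatment-emergent corneal event | Worst value and change between start and end of the event | Can be kept, although the lead-in sentence says otherwise |
| ECG done on days 22-30 | Inside the period | Counted |
| Schirmer | Baseline status only | Not relevant |
| Slit lamp | Baseline and corneal-event time points | Not tied to day 30 |

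**Direction for laboratory values.** A worst grade is a maximum. Leaving a value out can lower it or leave it unchanged, never raise it. The number of participants at or above any grade is thus correct or too low.

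**Number of visits that could be involved.** Assume every treated participant has an EOT visit and that 10% to 50% of visits fall on days 31-35 (both are assumptions). The range is 30 × 0.10 = 3 visits to 36 × 0.50 = 18 visits. This counts visits, not changed table entries. An entry changes only when the late value is worse than all that participant's earlier on-treatment values.

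**The case against.** The strongest defence is that 30 days is a coherent, pre-specified boundary. It matches protocol 9.4.2, and protocol 9.4.2.4 bases worst laboratory grade on the same treatment period. One boundary for adverse events and measurements avoids calling the same day-33 finding on-treatment in one table and post-treatment in another. Laboratory tests are also drawn every cycle, hematology weekly early on, and severe neutropenia and liver abnormalities are rechecked every 2 to 3 days, so many worst values will already have been seen. Post-treatment AEs and SAEs are reported separately, and the study is descriptive with no testing.

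All of this limits the effect. None of it explains why a measurement taken on a permitted day should be left out of the summary of a secondary endpoint.

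Several stronger readings are tempting and are not supported:
- That every worst-on-treatment safety analysis is affected. The table above shows otherwise for Schirmer, slit lamp and the corneal-event BCVA tables.
- That EOT ECGs are lost. One done to the ECG-specific rule is always counted. A day 31-35 ECG fits only the general EOT column, which is a conflict between two windows in the protocol.
- That corneal toxicity goes undetected. The flow chart schedules ocular tests only at screening and EOT, but protocol 8.2.2 and 8.2.6.2 also require complete tests whenever symptoms occur, with weekly repeats. Corneal event rates come from coded adverse events, whose window is not in question here.
- That 45% of EOT data are discarded. 5/11 is a share of calendar days. Reading it as a share of visits assumes evenly spread visits, and EOT is brought forward when another anticancer therapy starts.
- That the lost values are often toxicity-related. The documents give no basis for this, and EOT falls about 30 days after the last dose, more than two 14-day cycles later.

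**Conclusion.** The mismatch is real and follows from the day counts alone. It affects laboratory worst grades and PCSA, worst vital-sign values and the all-participants BCVA tables. For laboratory grades the direction is known: unchanged or understated. The size is not known, because it depends on how many EOT visits fall on days 31-35 and how often such a value is the participant's worst, and the documents inform neither. In a descriptive single-arm study of about 30 to 36 participants this is a modest defect, worth correcting because the correction is cheap. Separately, the EOT ECG window and the EOT visit window contradict each other, and the lead-in to the BCVA tables does not agree with the event-date rule that follows it.

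**What to change.** 1. In SAP 4.1 and 4.7.3, for scheduled visit-based measurements only, count the EOT assessment as on-treatment when it is done within its protocol window (to last IMP + 35 days) and before any further anticancer therapy. Leave the TEAE window at last IMP + 30 days.
2. Record this as a clarification to protocol 9.4.2 and 9.4.2.4, which use the 30-day period. The different wording in protocol 8.3.1 can be aligned at the same time.
3. In SAP 4.7.3.2, align the on-treatment lead-in with the event-date rule for the corneal-event BCVA tables.
4. Reconcile the EOT ECG window (days 22-30) with the EOT visit window (days 25-35). The triplet flow chart carries the same pair of windows, so any analysis plan for that cohort needs the same attention.

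The cost is a sentence or two in the SAP and a visit-mapping rule that uses dates only. No new data are needed, and it can be settled before database lock. The downside is that a few more abnormal values may count as on-treatment, and a day 31-35 laboratory abnormality may be on-treatment while the related adverse event is post-treatment. A table footnote would cover that.
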